5.2.1 Intent-to-Treat Population (ITT)

The ITT population will include all randomized/enrolled subjects. All efficacy data will be analyzed using the ITT population for US FDA. If actual treatment received differs from the randomized treatment arm, the randomized treatment arm will be used for analysis for the ITT.

ITT1 is a subset of ITT which includes all subjects randomized/enrolled prior to Amendment 2. ITT2 is a subset of ITT which includes all randomized/enrolled subjects under Amendment 2 or later.

5.2.2 Safety Population

The Safety population will include all subjects who took any dose of study medication. All safety data will be analyzed using the safety population. If actual treatment received differs from the randomized treatment arm, the actual treatment arm will be used for analysis for the Safety population.

5.2.3 Full Analysis Set (FAS)

The FAS consists of all randomized/enrolled subjects who received at least one dose of study drug and have baseline and at least one post-dose Hb assessment. If actual treatment received differs from the randomized treatment arm, the randomized treatment arm will be used for analysis for the FAS except for analyses by maintenance dosing frequency which will be presented as-treated. This analysis set is primarily used for EX-US submissions.

FAS1 is a subset of FAS subjects who are randomized/enrolled prior to Amendment 2. FAS2 is a subset of FAS subjects who are randomized/enrolled under Amendment 2 or later.

5.2.4 Per Protocol Set (PPS)

All randomized/enrolled subjects who receive at least 8 weeks of study treatment, have valid corresponding Hb measurements, and are without major protocol violations. The PPS population will be utilized for supportive analysis of primary endpoints.

PPS1 is a subset of PPS subjects who are randomized/enrolled prior to Amendment 2. PPS2 is a subset of PPS subjects who are randomized/enrolled under Amendment 2 or later.

All primary and secondary efficacy analyses will be based on the ITT (for US FDA) or FAS (for EMA) population as the primary analysis set respectively. Primary and secondary analyses will be repeated using the FAS or ITT respectively as supportive sensitivity analyses. Additional efficacy analyses will use the FAS as specified in the TLF (Tables, Listings and Figures) index.

5.3 METHODOLOGY AND CONVENTIONS

Continuous variables will be presented by descriptive statistics: n, mean, standard deviation, median, minimum, and maximum. Categorical variables will be presented by frequency count and percentage.

Lab results obtained from the central laboratory, rather than local laboratories, will be used for all efficacy and safety analyses. Local laboratory values, if collected in the CRF's, will be listed.

The treatment groups will be presented as follows:

Roxadustat QW(1A), Roxadustat BIW(2A), Roxadustat TIW(3A), Pooled Roxadustat (1A+2A+3A), Pooled Placebo (1P+2P+3P). Most safety and efficacy tables will be presented by Pooled Roxadustat vs. Pooled Placebo. Selected safety and efficacy tables will present randomized treatment arms of QW, BIW and TIW if the patient received the actual maintenance dosing frequency for QW, BIW and TIW. In these tables, Roxadustat subjects who were randomized to BIW or QW under Amendment 1 but never switched (e.g., due to Amendment 2) to that maintenance frequency will not be presented in BIW or QW group, but in the TIW and pooled Roxadustat groups.

The statistical comparisons will be done between roxadustat against Placebo as deemed appropriate, where the groups before amendment 2 are pooled

Unless otherwise stated, all statistical tests will be two-sided hypothesis tests performed at the 5% level of significance for main effects and all confidence intervals will be two-sided 95% confidence intervals.

The primary and secondary endpoints will be tested sequentially using the fixed sequence approach for multiplicity adjustments at an alpha level of 0.05. There will be no adjustments for multiple comparisons for other tests.

All analyses will be performed using SAS[®] Version 9.1.3 or higher.

5.4 ADDITIONAL DATA HANDLING RULES AND PRESENTATION SPECIFICATIONS

The following general guidelines will apply to all statistical analyses and data presentations:

- Baseline is defined as the last available value obtained prior to the first dose of study drug, unless otherwise specified in this SAP.
- Hb baseline is defined as the mean of the last four available values obtained prior to the first dose, including the Day 1 pre-dose value.
- eGFR and urine albumin-to-creatinine ratio (UACR) baseline will use the mean of all available central lab values prior to the first dose of study drug, including the Day 1 pre-dose value.
- Baselines for reticulocyte count, reticulocyte hemoglobin content (CHr), hepcidin, hs-CRP, serum iron parameters (transferrin, TIBC, TSAT, Ferritin, sTfR, and iron), blood pressures and heart rate are defined as the mean of values obtained within two weeks prior to the first dose.
- Randomization stratification factors derived from actual data (not the ones from the randomization system) will be used in all applicable analysis models. A table will show the discrepancies between the two.
- Analysis visits (instead of the nominal visits from CRF) derived from visit dates and visit time windows will be used in all analyses, tables, listings and figures. Unscheduled visits within an allowable window will be grouped into the closest scheduled visits based on the visit window specified in Appendix 1. For subjects who have more than one measurement at a scheduled visit, the last measurement will be used, with the exception of CPK, WBC, liver function tests (i.e., ALT, AST, GGT, ALP, and total bilirubin), in which the maximum measurement will be used.

- By default, US conventional units will be used for laboratory value presentations. A set of lab summary tables in SI units will also be provided based on TLF index.
- Age is calculated as of date that the informed consent form was signed.
- age = INTCK('YEAR', Birth Date, Date of Informed Consent, 'C')
where INTCK is a SAS function.
- Duration of treatment or days in treatment is calculated as: last dose date – first dose date +1
- Body weight, height and temperatures will converted using the following formula:
 - kg = lb/2.2
 - cm = 2.54 x in
 - C° = (5/9) x (F° – 32)
- eGFR will be calculated using the following Modification of Diet in Renal Disease (MDRD) equation:
$$\text{eGFR (in mL/min per 1.73m}^2\text{)} = 175 \times (\text{S}_{\text{Cr}} \text{ in mg/dL})^{-1.154} \times (\text{Age in years})^{-0.203} \times (0.742 \text{ if female}) \times (1.212 \text{ if African American})$$

where S_{Cr} = serum creatinine concentration
- Mean Arterial Pressure (MAP) will be derived using the following equation:
$$\text{MAP} = (2/3) * \text{DBP} + (1/3) * \text{SBP}$$
- For continuous variables that are recorded as “<X” or “>X”, the value of “X” will be used in the calculation of summary statistics.
- The mean, standard deviation and median will be presented with adding one more decimal to raw data with rounding off. The minimum and maximum will be presented with the same number of decimals as in the raw data.
- All percentages will be rounded to one decimal place and lined up by the decimal place. The percentage will be suppressed when the count is zero.
- Any p-values will be rounded to four decimal places and will be presented as ‘<.0001’ if they are less than 0.0001 before rounding.
- All tables and listings will have a header showing “FibroGen, Inc.”, the protocol number, date of the database transfer, and Page x of y. A footer will show the program file path/name, output file path/name, run date and run time.
- Additional data handling conventions are detailed in Appendix 1.

6 SUBJECT ACCOUNTABILITY AND DISPOSITION

The number of subjects included in each study population (i.e., ITT, Safety, FAS, and PPS) will be summarized by treatment group. The table will be repeated for subjects randomized/enrolled under Amendment 2 or later.

The number and percentage of subjects completed (through treatment and through end of study) and prematurely discontinued during the double-blind period and overall (including pre-dose and follow-up periods) will be presented for each treatment group and overall for the randomized population. Reasons for premature discontinuation from treatment as recorded on the disposition CRF will be summarized (number and percentage) by treatment group for the randomized population. Percentage of premature study drug discontinuations will be compared between treatment groups (roxadustat overall vs. placebo) using *Fisher's Exact Test*.

All subjects who prematurely discontinued from treatment or study will be listed by discontinuation reason and point of discontinuation (pre-dose, double blind treatment, or follow-up period) for the randomized population.

7 PROTOCOL DEVIATIONS

Important protocol deviations of interest may include, but are not limited to, the following:

- Subjects who did not meet inclusion/exclusion criteria
- Subjects who received disallowed concomitant medications or non-drug therapy
- Subjects who missed more than 25% doses of prescribed study medication during the overall treatment period.

The number and percentage of important protocol deviations will be categorized and tabulated as appropriate. A subset of pre-specified major protocol deviations will exclude some patients in the PPS analyses. These will be identified prior to database lock and unblinding. Considerations will be given according to the following table.

Table 2. Criteria for Assessing Major Protocol Deviations

Number	Major Protocol Deviation
1	Violation of key* inclusion or exclusion criteria which may affect the assessment of the efficacy of the study drug
2	Administration of wrong randomization study drug for more than 1 week
3	Study drug compliance < 75% (up to Week 52)
4	Administration of prohibited concomitant medication that may impact evaluation of efficacy of the study drug*
5	Significant noncompliance with study procedures that may impact evaluation of efficacy of the study drug will be evaluated case by case*

* Subject to Medical Monitor's decision

8 DEMOGRAPHICS AND OTHER BASELINE CHARACTERISTICS

Demographic parameters and important baseline and disease characteristics including randomization stratification factors will be summarized by treatment group for the ITT, ITT1, ITT2, Safety, FAS, FAS1, FAS2, and PPS populations. These include but may not be limited to age and age group, sex, ethnicity, race, weight, body-mass index (BMI), Hemoglobin, Ferritin and Ferritin group (≤ 100 vs. >100 ng/mL), TSAT and TSAT group ($\leq 20\%$ vs. $>20\%$), iron repletion status ([TSAT $\geq 20\%$ and ferritin ≥ 100 ng/mL] vs. others), baseline C-reactive protein (CRP) group (CRP \leq ULN vs. CRP $>$ ULN), eGFR and eGFR group (<10 , 10 - <15 , 15 - <30 , 30 - <45 , 45 - <60 , and ≥ 60 mL/min/1.73m²).

Descriptive statistics (n, mean, standard deviation, median, minimum, and maximum) will be presented for continuous variables. In addition, 25%-75% values of Hb and platelets will be presented. Frequency distributions (number and percentage of subjects) will be presented for categorical variables.

Descriptive statistics of baseline values for other parameters will be presented in their change from baseline tables.

Comparability of baseline characteristics among treatment groups will be tested using analysis of variance (ANOVA) model for continuous variables and Chi-Square test for categorical variables for guidance only.

9 MEDICAL HISTORY

Medical History of interest including but not limited to Chronic Kidney Disease (CKD) History inclusive of CKD Cause, Cardiovascular Disease, Cerebrovascular Disease, Thrombosis History, Diabetes History, and Anemia History will be summarized by treatment group for the Safety Population.

10 STUDY MEDICATION

10.1 EXTENT OF EXPOSURE

Exposure to study medication will be summarized in terms of treatment duration, which is calculated as the number of days from the date of first double-blind medication taken to the date of last dose taken, inclusively.

Total weekly study drug exposure is defined as the total prescribed dose (in mg or mg/kg) of study drug administered within the week (per CRF dosing week).

Duration of exposure, weekly exposure and total study drug exposure will be tabulated by treatment group and overall for the safety population.

Per dose amount and dosing frequency for every four-week period will also be tabulated by treatment group for the Safety population.

Patient-Exposure-Year (PEY) is defined as $(\text{Last Dose Date} - \text{First Dose Date} + 1)/365.25$.

Patient-Followup-Year (PFY) is defined as $(\text{Last Dose Date} - \text{First Dose Date} + 28)/365.25$.

10.2 DOSE ADMINISTRATION

Summary of weekly dose (in mg and mg/kg) immediately prior to Hb correction target achieved, weekly dose and dose per intake after Hb correction target achieved (in the 1st, 4th, 8th, 12th weeks, and Weeks 49-52) will be tabulated. Number of dose adjustments by type and overall before and after Hb correction (within 8 weeks and throughout treatment period up to Week 52) will be summarized.

10.3 TREATMENT COMPLIANCE

Study medication compliance for a specified period is defined as the total dose (mg) actually taken by a patient during that period divided by the prescribed dose expected to be taken during the same period multiplied by 100. Descriptive statistics for study medication compliance will be presented by treatment group for the whole double-blind period of the study.

11 PRIOR AND CONCOMITANT MEDICATIONS

The World Health Organization Drug Dictionary (WHODD) Version 15 will be used to classify prior and concomitant medications by therapeutic class and preferred term based on ATC code level 3. Prior medication is defined as any medication taken and stopped prior to the first dose of the study medication. Concomitant medication is defined as any medication taken between the day of first dose of the study medication and the day of last study medication date + 28 days, inclusive.

Medication start and end dates will be compared with the start date of study drug and classified as per Table 3. In case of partial or missing dates, comparisons will be made based on the level of details available. For example, if start date of study drug infusion is 04Jan2013, and a medication has a start date of 04Jan2013, the medication will be classified as concomitant. A start date of Jan2013 (i.e., missing day) would also see the medication classified as concomitant.

Table 3. Classification of Prior and Concomitant Medications

Start Date \ End Date	Before start of study drug administration	On or after start of study drug administration	Missing
Before start of study drug administration	Prior	Concomitant	Concomitant
On or after start of study drug administration	Prior	(Treatment Emergent) Concomitant	(Treatment Emergent) Concomitant
Missing	Prior	Concomitant	Concomitant

Both prior and concomitant medication usage will be summarized by the number and proportion of subjects in each treatment group receiving each drug within each therapeutic class using the safety population. Multiple drug usage by a patient will be counted only once.

Detailed analyses may be performed on prior and concomitant medications of special interests such as oral iron, blood pressure medications and lipid medications based on TLF shells.

12 EFFICACY ANALYSES

Hemoglobin results obtained from the central laboratory will be used for all efficacy analyses.

Baseline Hb is defined as the mean of the last four central laboratory Hb values prior to the first dose of study treatment. Hemoglobin values after a rescue therapy will not be excluded for the US (FDA) submission primary efficacy analysis. Hemoglobin values within 6 weeks after a rescue therapy will be excluded for the Ex-US submission primary efficacy endpoint as well as some sensitivity efficacy analyses.

The **Efficacy Emergent Period** is defined as the evaluation period from the Analysis date of first dose intake up to 7 days after the Last Dose of study drug or EOT Visit, whichever occurs first. This period will be used as reference period for the time to event analyses related to efficacy endpoints, unless specified otherwise.

12.1 PRIMARY ANALYSIS

For US (FDA) Submission

The primary US FDA efficacy endpoint will be analyzed using the ITT population as the primary analysis population.

The primary efficacy endpoint for the US (FDA) submission is the Hb CFB to the average level during the evaluation period, defined as Weeks 28 to 52.

The rationale for choosing the specified evaluation period as the primary endpoint for US (FDA) submission is that one would expect to have achieved Hb correction by Week 28, and averaging it to Week 52 would be an accurate reflection of a longer term therapeutic effect of roxadustat.

The hypothesis to be tested for the primary efficacy analysis is:

H_0 : Hb CFB to the average of Weeks 28 to 52 in the roxadustat group = Hb CFB to the average of Weeks 28 to 52 in the placebo group

Versus:

H_1 : Hb CFB to the average of Weeks 28 to 52 in the roxadustat group \neq Hb CFB to the average of Weeks 28 to 52 in the placebo group

The efficacy endpoint will be defined as each patient's Hb change from baseline to the average level during the evaluation period, defined as Week 28 to 52 of the treatment period. A Multiple Imputation Analysis of Covariance model (MI ANCOVA) will be used to test the primary hypothesis. The model will contain terms for baseline Hb and baseline eGFR measurements as covariates and treatment arm and the other randomization stratification factors except screening Hb (≤ 8 vs > 8) and eGFR factor as fixed effects.

The MI ANCOVA model will be used to compare the pooled roxadustat and pooled placebo groups: Pooled roxadustat (TIW+BIW+QW) vs. pooled placebo. Efficacy by maintenance dosing frequency (i.e., TIW, BIW, QW vs. pooled placebo) will also be evaluated using FAS.

H_0 will be tested at the two-sided alpha = 0.05 level of significance and will be rejected if the $p < 0.05$ from the test.

The following steps will be used to conduct the primary analysis.

1. Generate 200 datasets, using seed 126345, where intermittent missing hemoglobin data will be imputed for each treatment relying on non-missing data from all subjects within each treatment group using the Monte Carlo Markov Chain MCMC imputation model with treatment, baseline hemoglobin, randomization stratification factors, and the available non missing hemoglobin for each scheduled Week.

The MCMC statement in the SAS PROC MI procedure with monotone option will be used. As a result, each dataset will only have missing ending data, or a monotone missing data pattern.

Sample SAS code:

```
PROC MI data=xx out=xx seed=xx nimpute=200;
  by treatment;
  var treatment covariates Week1 ... Week 52;
  mcmc impute=mono;
run;
```

2. For each dataset from step 1, missing ending data (hemoglobin up through end of evaluation period) will be imputed using seed 472794. As a result, 200 imputed complete datasets will be generated.
 - Missing data at Week 1 will be imputed using the regression imputation model with baseline stratification factor, baseline and hemoglobin from Week 1, using the SAS PROC MI procedure with the REGRESSION option in the MONOTONE statement.

- The SAS PROC MI procedure will use data separately from each treatment subject to impute the missing data for a specific Week (i.e., only those that need the imputation for the Week). Since subjects from the different treatment groups for that Week are excluded from the step, they will not contribute to the imputation for the Week.
- Repeat for all other scheduled Weeks sequentially (Week 2 to the end of evaluation period). Subjects whose missing data were imputed for previous Weeks will contribute to the imputation for the current Week.

The regression imputation model includes an intercept and the slopes of the hemoglobin from previous Weeks and the stratification factors.

3. Analyze each imputed dataset using the analysis of covariance model (ANCOVA) using the mean of all observed or imputed Hb values within the evaluation period. The model will contain terms for baseline Hb and eGFR measurements as covariates and treatment arm and the other randomization stratification factors except baseline Hb (≤ 8 vs > 8) and eGFR as fixed effects.

Sample SAS code:

```
PROC MIXED data=xx;  
  class treatment categorical covariates;  
  model change_Week36 = treatment covariates / solution;  
  lsmeans treatment / diff cl;  
  ods output Diffs=lsdiffs LSMeans=lsm solutionF=Parms;  
  by _Imputation_ ;  
run;
```

4. Combine estimates from the results of each of the 200 ANCOVA runs using SAS PROC MIANALYZE.

Sample SAS code:

```
PROC MIANALYZE parms(classvar=full)=lsdiffs;  
  class treatment categorical covariates;  
  modeleffects treatment;  
  ods output ParameterEstimates=MIAN_ lsdiffs;  
run;
```

Report the results of the least-squares mean estimates of the change from baseline in hemoglobin during the evaluation period, the estimates of treatment effect (e.g. least-squares mean CFB in

hemoglobin for the treatment group minus the least-squares mean CFB in hemoglobin for the placebo group) and the corresponding p-values and 95% CIs during the evaluation period.

For Ex-US Submission

The primary EX-US efficacy endpoint will be analyzed using the FAS population as the primary analysis population.

The primary efficacy endpoint for the Ex-US submission of proportion of responders will be compared using Cochran-Mantel-Haenszel (CMH) adjusting for the randomization stratification factors comparing the pooled roxadustat (TIW+BIW+QW) to pooled placebo (TIW+BIW+QW). The hypothesis to be tested for the primary efficacy analysis is:

H₀: Hb responder rate in the roxadustat group = Hb responder rate in Placebo group

Versus:

H₁: Hb responder rate in the roxadustat group ≠ Hb responder rate in Placebo.

H₀ will be tested at the two-sided alpha = 0.05 level of significance and will be rejected if the p < 0.05 from the test.

The SAS procedure will be similar to the following:

```
proc freq;
  tables covariates*Treatment*Response / cmh;
run;
```

The 95% CIs based on CMH adjusted odds ratio will be reported. In addition, the 95% CIs of the responder rate and rate difference between treatment groups based on the exact method of Clopper-Pearson will be calculated and presented.

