9.4.3.1 Primary Efficacy Analysis

The primary efficacy endpoint will be analyzed using the ITT population as the primary analysis population and PPS population as a supportive analysis population.

For US (FDA) Submission

The primary efficacy endpoint for the US (FDA) submission is the Hb CFB to the average level during the evaluation period, defined as Weeks 28 to 52.

The planned treatment duration is at least 52 weeks. The rationale for choosing the specified evaluation period as the primary endpoint for US (FDA) submission is that one would expect to have achieved Hb correction by Week 28, and averaging it to Week 52 would be an accurate reflection of a longer term therapeutic effect of roxadustat.

The hypothesis to be tested for the primary efficacy analysis is:

H_0 : Hb CFB to the average of Weeks 28 to 52 in the roxadustat group = Hb CFB to the average of Weeks 28 to 52 in the placebo group

Versus

H_1 : Hb CFB to the average of Weeks 28 to 52 in the roxadustat group = Hb CFB to the average of Weeks 28 to 52 in the placebo group

A Multiple Imputation Analysis of Covariance model (MI ANCOVA) will be used to compare the roxadustat and pooled placebo groups in a fixed sequence procedure: 1) pooled roxadustat (TIW+BIW+QW) vs. pooled placebo, 2) roxadustat TIW vs. pooled placebo, 3) roxadustat BIW vs. pooled placebo, 4) roxadustat QW vs. pooled placebo. The latter are being performed to test the BIW and QW maintenance dosing frequencies that are enrolled from earlier versions of the protocol. If a null hypothesis is rejected, the claim of the tested roxadustat regimen over placebo will be declared successful and the test will progress to the next comparison in sequence.

H_0 will be tested at the two-sided alpha = 0.05 level of significance and will be rejected if the $p < 0.05$ from the test.

Hemoglobin values under the influence of a rescue therapy will not be censored in the primary analysis. The model will contain terms for treatment arm, baseline measurement, visit, visit by treatment arm, and other randomization stratification factors. The primary efficacy analysis will be based on the estimated difference in the overall mean effect between the two treatment groups throughout the evaluation period based on the MI ANCOVA model.

For Ex-US Submission

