3 STUDY DESIGN

This is a Phase 3, multi-center, randomized, double-blind, placebo-controlled study in anemic subjects with Stage 3, 4, or 5 CKD who are not on dialysis.

This study will consist of three study periods:

- **Screening Period:** Up to 6 weeks
- **Treatment Period:** Variable for individual subjects. In order to complete the Treatment Period simultaneously for all study subjects, the minimum treatment duration may be less than 52 weeks, with a maximum treatment duration of up to 3 years after the last subject is randomized.
- **Post-Treatment Follow-Up Period:** 4 weeks

3.1 IN ORIGINAL PROTOCOL AND AMENDMENT 1

Following the Screening Period, subjects are randomized to 1 of 6 treatment arms, defined by their dose frequency during maintenance (see Table 1). The randomization will result in a 2:2:2:1:1:1 ratio of subjects receiving roxadustat or placebo, respectively.

Randomization stratification factors include screening Hb values, cardiac/cerebrovascular/thromboembolic medical history, and estimated glomerular filtration rate (eGFR), and geographic region.

The Investigator, study site staff, subject, and the sponsor, are blinded to study drug, but not to dose or dosing frequency. Additionally, all efforts will be made to keep subjects blinded to study Hb values.

Study drug will be dosed TIW for anemia correction until subjects achieve a Hb value of ≥ 11 g/dL and ≥ 1 g/dL increase from baseline at two consecutive visits. Once these criteria are met, a dose frequency conversion to QW or BIW or a continuation of TIW will occur according to the subject's assigned treatment arm at randomization, defining entry into the maintenance phase.

Table 1. Study Drug Dose Frequencies

Treatment Arms	Correction	Maintenance	n (Roxadustat)	n (Placebo)
1A	TIW	QW	100*	0
1P	TIW	QW	0	50*
2A	TIW	BIW	100	0
2P	TIW	BIW	0	50
3A	TIW	TIW	100	0
3P	TIW	TIW	0	50

A=Active, P= Placebo

*These numbers are based on a sample size of 450 and would increase if overall sample size increases.

3.2 UNDER AMENDMENT 2 & 3

Following the Screening Period, subjects will be randomized in a 2:1 ratio to receive roxadustat (approximately 300-800 subjects) or placebo (approximately 150- 400 subjects). Randomization is stratified by the following factors:

- Screening Hb values (≤ 8 g/dL vs > 8 g/dL)
- History of cardiovascular, cerebrovascular or thromboembolic diseases (Yes vs No)
- eGFR (< 30 mL/min/1.73 m² vs ≥ 30 mL/min/1.73 m²)
- Geographic region (US vs Ex-US).

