Subjects who were randomized after the implementation of Amendment 2 or those who were previously randomized but had not been changed to BIW or QW for maintenance treatment will be dosed TIW throughout the study; subjects who have already converted to BIW or QW dosing regimens as a result of being enrolled under previous Study FGCL-4592-060 protocol versions and were converted to BIW or QW during maintenance phase will continue respective maintenance dosing frequencies. Starting doses of study drug will be dose adjusted according to anemia correction guidelines in the protocol until subjects achieve a Hb value of ≥ 11 g/dL and ≥ 1 g/dL increase from baseline by central lab (single occurrence). Once these criteria are met, subjects will enter into the maintenance phase of anemia treatment and will be dose-adjusted according to maintenance guidelines.

Study drug dose will remain constant during the first 4 weeks of the Treatment Period, unless a dose reduction is required for Excessive Hematopoiesis (EH). Dose adjustments are permitted starting at Week 4, and at intervals of every 4 weeks thereafter.

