5 GENERAL STATISTICAL CONSIDERATIONS

5.1 SAMPLE SIZE DETERMINATION

A total of at least 450 and up to 1200 planned subjects will be randomized in a 2:1 ratio to receive either roxadustat (at least 300, but at most 800 subjects) or placebo (at least 150, but at most 400 subjects) in a double-blind manner.

The study is sufficiently powered for both regionally-based primary efficacy endpoints. A minimum of 450 subjects are planned to be randomized to receive roxadustat or placebo (2:1 with approximately a minimum of 300 roxadustat vs 150 placebo) in a double-blind manner in order to support the primary endpoint(s) of the study.

For US (FDA) Submission Primary Efficacy Endpoint

A sample size of 450 will have > 99% power to detect a 0.75 g/dL difference in mean Hb values between the two treatment groups, assuming that the common standard deviation is 1.2 g/dL, using an analysis of variance (ANOVA) test with a 0.05 two-sided significance level.

For the comparisons of individual treatment arms for each of the 3 dose frequencies of roxadustat for Hb maintenance versus pooled placebo, a sample size of 35 roxadustat and 150 placebo will have 90% power to detect a 0.75 g/dL difference in mean Hb values between the

two treatment groups, assuming that the common standard deviation is 1.2 g/dL, using an ANOVA test with a 0.05 two-sided significance level.

For Ex-US Submission Primary Efficacy Endpoint

Based on a two-sided test at the $\alpha = 0.05$ level of significance, 450 subjects will have > 95% power to demonstrate a statistically significant difference between roxadustat and placebo, assuming that the proportion of subjects with a Hb response in the roxadustat group is at least 65% and the proportion of subjects with a Hb response in the placebo group is at most 25%.

During the course of this Phase 3 study, which is being conducted in parallel with other Phase 3 studies, up to 1200 subjects may be enrolled in this study to support the overall safety evaluation of roxadustat across pooled multiple studies in the Phase 3 program, including adjudicated composite safety endpoints of interest. The study will stop enrollment at the Sponsor's discretion if:

- 1) The minimum of 450 subjects has been achieved to support the primary endpoint in this individual study, and

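### BIW and QW roxadustat subjects were all randomised before Amendment 2, but their placebo comparator appears to include later placebo subjects, with no adjustment for enrolment era.

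*SAP*

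**What the plan says.** **Who can be BIW or QW.** SAP 3.1 describes six arms before Amendment 2: "The randomization will result in a 2:2:2:1:1:1 ratio of subjects receiving roxadustat or placebo, respectively". From Amendment 2 (SAP 3.2) allocation is 2:1 roxadustat to placebo. The group described as "Subjects who were randomized after the implementation of Amendment 2" is dosed TIW throughout, and only subjects already converted stay on BIW or QW. SAP 12.3 item 4 confirms that arms 2A and 1A come from the first two protocol versions.

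**The comparator.** SAP 12.1 uses pooled placebo for the whole-trial primary test and then, in the next sentence, for the frequencies: "Efficacy by maintenance dosing frequency (i.e., TIW, BIW, QW vs. pooled placebo) will also be evaluated using FAS". SAP 5.2.3 puts no amendment cut on the FAS. It does define the subset needed: "FAS1 is a subset of FAS subjects who are randomized/enrolled prior to Amendment 2". The SAP text assigns ITT1 and FAS1 only to the baseline tables (SAP 8). The sensitivity analyses in SAP 12.2 use ITT2 and FAS2.

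**The model.** The MI ANCOVA adjusts for baseline Hb, baseline eGFR and the remaining stratification factors (region, cardiovascular history). The CMH test uses the stratification factors. Neither has an era term.

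**Where the comparisons count.** Protocol 9.4.3.1 lists "3) roxadustat BIW vs. pooled placebo, 4) roxadustat QW vs. pooled placebo" as the last steps of the US primary sequence. SAP 12.1 no longer contains that sequence, but SAP 12.3 item 4 tests TIW, BIW and QW against pooled placebo within the secondary fixed sequence, ahead of items 5 to 12.

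**The concern.** A placebo subject randomised after Amendment 2 had no chance of being assigned BIW or QW. Used as a control for those groups, that subject is non-concurrent, and randomisation does not protect this part of the contrast.

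The documents show that conditions changed over time. The rule for entering maintenance differs between SAP 3.1 (two consecutive visits) and SAP 3.2 (a single occurrence). Protocol 10.3.7 and Appendix 1 record different maximum doses and dose steps under earlier versions. The ESA and IV iron rescue criteria refer to dose increases or the maximum dose (Protocol 4.6.2.2 and 4.6.2.3), so rescue in placebo subjects could also differ by era. None of this shows that drift occurred, but absence of drift should not be taken for granted.

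At stake are the BIW and QW effect estimates. In SAP 12.3 item 4, bias in one direction could support a frequency claim and release later tests; in the other it could block items 5 to 12. A fixed sequence controls error only if each test in it is valid.

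**Working it through.** **Inputs from SAP 5.1 and 3.** Two-sided alpha 0.05; "a sample size of 35 roxadustat and 150 placebo will have 90% power to detect a 0.75 g/dL difference in mean Hb values", "assuming that the common standard deviation is 1.2 g/dL"; allocation 2:2:2:1:1:1 before Amendment 2 and 2:1 afterwards; placebo total 150 to 400; planned arms of 100 against 150 pooled placebo at N = 450.

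**Not in the documents, so assumed.** The between-era drift in placebo Hb change, and the share of placebo randomised before Amendment 2.

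**1. The plan's own power figure.** SE = 1.2 × √(1/35 + 1/150) = 0.225, and 0.75 / 0.225 = 3.33. Power is 91.5% by normal approximation and 91.2% by noncentral t. The stated 90% reproduces.

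**2. Which comparisons are exposed.**
- Pooled roxadustat versus pooled placebo: (2+2+2):(1+1+1) = 2:1 before Amendment 2 and 2:1 after. Both sides have the same era mix, so drift common to both groups cancels.
- BIW or QW versus pooled placebo: active subjects are 100% early and placebo is a mixture. Bias = drift × non-concurrent share of placebo.
- TIW: both eras contribute on both sides. For example, take 400 placebo of whom 100 are early. By randomised arm, early TIW is about 67 (100 × 2/3) and later TIW is 600 (300 × 2), so 10% of TIW is early against 25% of placebo. A common drift of 0.2 g/dL gives a bias of 0.2 × 0.15 = 0.03 g/dL in size, against 0.2 × 0.75 = 0.15 for BIW or QW.

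**3. Illustrative type I error for BIW or QW.** With s = bias / SE, type I error = Φ(−1.96 − s) + 1 − Φ(1.96 − s). For 35 versus 400, SE = 1.2 × √(1/35 + 1/400) = 0.212. For 100 versus 400, SE = 0.134.

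| Arm vs placebo | Concurrent placebo | Assumed drift (g/dL) | Bias (g/dL) | Type I error |
|---|---|---|---|---|
| 35 vs 400 | any | 0 | 0 | 5% |
| 35 vs 400 | 50% | 0.2 | 0.10 | 7.6% |
| 35 vs 400 | 25% | 0.2 | 0.15 | 10.9% |
| 35 vs 400 | 25% | 0.3 | 0.225 | 18.6% |
| 100 vs 400 | 150 of 400 | 0.2 | 0.125 | 15.4% |

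A larger arm makes a given bias matter more, because the SE is smaller.

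**4. Precision with concurrent placebo only.** Before Amendment 2 there are three placebo subjects for every two in one active arm, so an arm of 35 implies 35 × 1.5 ≈ 53. If the 35 are only those who converted, the concurrent placebo group is larger. Power at 0.75 g/dL, SD 1.2, noncentral t:

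| Arm vs placebo | Power |
|---|---|
| 35 vs 53 | 81.0% |
| 35 vs 100 | 88.5% |
| 35 vs 150 | 91.2% |
| 100 vs 150 | 99.8% |
| 35 vs 400 (all placebo) | 94.3% |

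**The case against.** **The comparator may already be the early placebo group.** The labels 1P, 2P and 3P are defined only in the pre-Amendment 2 arm table, SAP 12.3 item 4 uses them, and SAP 5.3 refers to pooling the groups from before Amendment 2. A reader might infer that the SAP plainly states that later placebo subjects enter; it does not. The narrower reading still fits poorly. The same term is the whole-trial primary comparator in the preceding sentence of SAP 12.1, SAP 5.3 pairs 1P+2P+3P with pooled roxadustat for most tables, and FAS rather than FAS1 is named. The text needs an edit on either reading.

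**These are minor comparisons.** This is partly right. In SAP 12.1 the frequency evaluation is an addition to the primary test, and Protocol 9.4.3.2 calls BIW and QW comparisons descriptive or exploratory. In the SAP they carry multiplicity weight only in 12.3 item 4, but there they do.

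**Covariates absorb drift.** Adjustment for baseline Hb, eGFR, region and cardiovascular history removes some of it, and the ITT1/ITT2 and FAS1/FAS2 baseline tables will show measured differences in case mix. Changes in rescue practice or other unmeasured factors remain.

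**The size is invented.** The drift and concurrent shares are indeed assumptions; 35 is a planning number and 400 the enrolment cap. Biases of 0.10 to 0.15 g/dL are also well below the planned 0.75 g/dL. The figures show sensitivity, not an expected error rate.

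**Concurrent placebo would not make the comparison randomised.** This stands. Analyses by frequency are as-treated (SAP 5.2.3), unconverted BIW and QW subjects move to TIW (SAP 5.3), and item 4 keeps only roxadustat subjects who responded. That selection is a separate and probably larger problem.

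**Conclusion.** The concern holds for BIW and QW only. On the most natural reading of SAP 12.1 and 12.3 item 4, these early-era groups are compared with placebo from both eras without an era term. If placebo Hb change differs by era beyond the adjusted covariates, the estimates are biased by that difference times the non-concurrent share. An assumed drift of 0.2 g/dL with 25 to 50% concurrent placebo puts the type I error for 35 versus 400 at about 8 to 11%; without drift it is 5%.

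Three stronger readings are not supported:
- That the primary result is compromised: allocation is 2:1 in both eras, so it is not.
- That the stated 90% power is wrong: it is correct for 35 versus 150. It carries over to a concurrent comparison only if about 150 placebo subjects were randomised before Amendment 2.
- That inflation has been shown: no document gives a drift or the number of placebo subjects randomised before Amendment 2.

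**What to change.** - In SAP 12.1 and 12.3 item 4 (and Protocol 9.4.3.1 if its steps 3 and 4 are kept), state which placebo subjects form the comparator for BIW and QW.
- Make that comparator FAS1 placebo (ITT1 where ITT is the analysis set). At minimum, add a before/after Amendment 2 factor to the ANCOVA and as a CMH stratum.
- Carry the same restriction or factor into the imputation step, because SAP 12.1 imputes within treatment group across all subjects.
- Report the all-placebo result as supportive.
- Beside the 35 versus 150 power figure, note that precision falls if fewer than 150 concurrent placebo subjects exist.
- Do not describe these comparisons as fully randomised; as-treated grouping and responder selection need their own remedy.

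The cost is SAP wording, since FAS1 and ITT1 already exist, plus some precision: power of about 81% for 35 versus 53 concurrent placebo, against 91% for 35 versus 150, and over 99% at the planned 100 versus 150.
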